3.1.2. Definition of Clinical Remission

- Definition per protocol: clinical remission is defined as SF subscore = 0 (or = 1 with a ≥ 1-point decrease from Baseline), RB subscore = 0, and endoscopic score (ES) ≤ 1 (excluding friability)
- Definition per FDA Draft Guidance: clinical remission is defined as SF subscore = 0 or = 1 and no greater than baseline, RB subscore = 0, and ES ≤ 1 (excluding friability), based on the 2022 FDA Draft Guidance; Ulcerative Colitis: Developing Drugs for Treatment.

The definition of clinical remission per FDA Draft Guidance will be used for the primary analysis.

3.1.3. Derivation of Clinical Remission

The primary efficacy endpoint is clinical remission at Week 52. Based on above different derivation algorithms for RB/SF subscores, and different definitions for clinical remission, the clinical remission will be derived based on the following 3 approaches, respectively:

- Clinical remission 1, based on clinical remission definition per protocol and RB and SF derivation per protocol (Derivation 1, Section 3.1.1)
- Clinical remission 2, based on clinical remission definition per FDA Draft Guidance and RB and SF derivation per protocol (Derivation 1, Section 3.1.1)
- Clinical remission 3, based on clinical remission definition per FDA Draft Guidance and RB and SF derivation per FDA Draft Guidance (Derivation 2, Section 3.1.1)

Clinical remission 2 will be used for the primary analysis.

3.2. Secondary Endpoint(s)

3.2.1. Efficacy Endpoint(s)

The study includes the following key secondary efficacy endpoints:

- Endoscopic improvement at Week 52. Endoscopic improvement is defined as ES ≤ 1 (excluding friability).
- 12-week corticosteroid-free clinical remission at Week 52: clinical remission at Week 52 and corticosteroid-free for ≥ 12 weeks immediately prior to Week 52. The 3 clinical remissions defined in Section 3.1.3 will be applied, respectively.

- Clinical remission at Week 12. The 3 clinical remissions described in Section 3.1.3 above will be applied.
- Endoscopic improvement at Week 12.
- Sustained clinical remission (clinical remission at both Weeks 12 and 52). The 3 clinical remission definitions defined in Section 3.1.2 will be applied, respectively.
- Histologic-Endoscopic Mucosal Improvement at Week 52. Histologic-Endoscopic Mucosal Improvement is defined as ES ≤ 1 (excluding friability) with Geboes Index score < 2.0.
- Complete symptomatic remission at Week 52. Complete symptomatic remission is defined as RB subscore = 0 and SF subscore = 0. Its derivation will be based on the following 2 approaches, respectively.
 - Complete symptomatic remission 1, based on RB and SF derivation per protocol (Derivation 1, Section 3.1.1)
 - Complete symptomatic remission 2, based on RB and SF derivation per FDA Draft Guidance (Derivation 2, Section 3.1.1)
- Complete symptomatic remission at Week 12. Two complete symptomatic remission definitions described above will be applied, respectively.

The study also includes the following other secondary efficacy endpoints.

- 12-week corticosteroid-free clinical remission at Week 52 among participants receiving corticosteroids at baseline: clinical remission at Week 52 and corticosteroid-free for ≥ 12 weeks immediately prior to Week 52. The 3 clinical remissions defined in Section 3.1.3 will be applied, respectively.
- 4-week corticosteroid-free clinical remission at Week 52: clinical remission at Week 52 and corticosteroid-free for ≥ 4 weeks immediately prior to Week 52. The 3 clinical remissions defined in Section 3.1.3 will be applied, respectively.
- 4-week corticosteroid-free clinical remission at Week 52 among participants receiving corticosteroids at baseline: clinical remission at Week 52 and corticosteroid-free for ≥ 4 weeks immediately prior to Week 52. The 3 clinical remissions defined in Section 3.1.3 will be applied, respectively.
- Clinical response at Week 12. Clinical response is defined as a ≥ 2-point and ≥ 30% decrease from baseline in MMS, and a ≥ 1-point decrease from baseline in RB subscore or an absolute RB subscore ≤ 1. Its derivation will be based on each of 2 derivations of RB and MMS in Section 3.1.1, respectively as follows:
 - Clinical response 1, based on RB and MMS derivation per protocol (Derivation 1, Section 3.1.1)

- Clinical response 2, based on RB and MMS derivation per FDA Draft Guidance (Derivation 2, Section 3.1.1)
- Clinical response at Week 52. Two clinical responses described above will be applied.
- Histologic-Endoscopic Mucosal Improvement at Week 12.
- Symptomatic remission at Week 52. Symptomatic remission is defined as SF subscore = 0 (or = 1 with a ≥ 1-point decrease from baseline) and RB subscore = 0. Its derivation will be based on the following 2 approaches, respectively.
 - Symptomatic remission 1, based on RB and SF per protocol (Derivation 1, Section 3.1.1)
 - Symptomatic remission 2, based on RB and SF derivation per FDA Draft Guidance (Derivation 2, Section 3.1.1)
- Symptomatic remission at Week 12. Two symptomatic remissions described above for symptomatic remission at Week 52 will be applied, respectively.
- Reduction from baseline in both ES and RB or in both ES and SF at Week 12.
 Derivations 1 and 2 for RB and SF described in Section 3.1.1 will be applied, respectively.
- Histologic response based on the Geboes Grading System at Week 12. Histologic response based on the Geboes Grading System is defined as Geboes Index score ≤ 3.1.
- Histologic response based on Robarts Histopathology Index (RHI) at Week 12.
 Histologic response based on RHI is defined as decrease in RHI of ≥7 points from baseline.

3.2.2. Safety Endpoint(s)

3.2.2.1. Adverse Event

AEs will be coded using MedDRA (v27.0). The version used to code AEs will be displayed in the analyses. Treatment-emergent adverse events (TEAEs) are defined as AEs that started or worsened in severity on or after the first dose of study treatment.

Refer to Section 9.1.5 for handling of partial dates for AEs for the purpose of assigning treatment-emergent flags. In the case where it is not possible to define an AE as treatment-emergent or not, the AE will be classified as treatment-emergent.

Severity of TEAEs

Severity is classified as Grade 1: Mild, Grade 2: Moderate, Grade 3: Severe, Grade 4: Lifethreatening, Grade 5: Death related to AE, using the Common Terminology Criteria for Adverse Events, v5.0 (CTCAE v5.0).

Relationship of TEAEs to Study Treatment

Relationship is classified as "not related", "unlikely related", "probably related", or "related" by the Investigator.

TEAEs Leading to Discontinuation of Study Treatment

TEAEs leading to discontinuation of study treatment will be identified by action taken being recorded as "Drug withdrawal" on the Adverse Events electronic case report form (eCRF).

Serious and Non-Serious TEAEs

Serious adverse events (SAEs) are those events recorded as "Serious" on the Adverse Events eCRF.

TEAEs Leading to Death

TEAEs leading to Death are those events which are recorded with an outcome as "Fatal" on the Adverse Events eCRF.

TEAEs of Special Interest

Categories of Targeted Medical Events (TMEs) and a list of preferred terms associated with these TME categories were developed based on the mechanism of action of etrasimod, prior experience with other agents acting via a similar mechanism, and disease-specific clinical judgment. The proposed candidate terms will be reviewed along with other supportive data (eg, vital signs, lab) to identify which events reflect AESI.

Categories and subcategories of TEAEs of special interest are the following:

- Cardiovascular Events
 - Bradycardia
 - AV conduction delay
 - Hypertension
- Macular Edema
- Pulmonary Disorders
 - Airflow obstruction (forced expiratory volume in 1 second [FEV1], forced vital

- capacity [FVC])
- Decrease gas exchange (diffusing capacity of the lungs for carbon monoxide
- [DLCO]
- Infections
 - Severe infections
 - Opportunistic infections (Narrow)
 - Herpes simplex and herpes zoster
- Liver Injury
 - Liver transaminases elevation
 - Bilirubin elevation
- Posterior Reversible Encephalopathy Syndrome (PRES)
- Malignancies

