5.1.1. Discontinuation from Double-Blind Treatment for Disease Worsening

Starting with the Week 12 assessment, subjects whose UC condition in the opinion of the Investigator has not improved or has worsened, compared with baseline (Week 0/Day 1), may be eligible to enroll in the OLE study (Study APD334-303) provided their ES is ≥ 2 and they meet one of the following entry criteria:

- RB subscore ≥ 2 at 2 timepoints at least 7 days and no more than 14 days apart
- RB + SF subscores ≥ 4 at 2 timepoints at least 7 days and no more than 14 days apart
- RB subscore ≥ 2 or RB + SF subscores ≥ 4 (in any order) at 2 timepoints at least 7 days and no more than 14 days apart

For subjects discontinuing prior to Week 52, an endoscopic evaluation is required to confirm eligibility for the OLE. An endoscopy should be performed upon the appearance of UC symptoms but no more than 14 days after the second timepoint for symptom criteria above. A proctosigmoidoscopy does not need to be repeated if performed within the last 4 weeks.

The Day 1 visit of the OLE study must occur within 14 days of the last on treatment visit of this study. In the event there is a gap between the last on treatment visit and W0/D1 of the OLE, the subject should continue their double-blind study treatment from Study APD334-210 until the day before the W0/D1 visit.

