9.9.9.2.2. Recording Adverse Events

The adverse event reporting period for safety surveillance begins when the subject is initially included in the study (date of first signature of informed consent) and continues up to 30 days after the last administration of study treatment. If an adverse event is not resolved or stabilized by this time, the Sponsor in consultation with the Investigator will decide whether to continue to monitor the adverse event or closeout the event in the database if no further follow-up is necessary.

Investigators are not obligated to actively seek information on AEs or SAEs after the subject has concluded study participation. Any SAE suspected to be related to the study treatment must be reported whenever it occurs, irrespective of the time elapsed since the last administration of study treatment.

Investigators and study personnel will record all adverse events and SAEs whether received through an unsolicited report by a subject, elicited during subject questioning, discovered during physical examination, laboratory testing, and/or other means by recording them on the eCRF and/or SAE Form, as appropriate. The following information should be recorded on the adverse event eCRF:

- Description including onset and resolution dates
- Whether it met SAE criteria
- Severity
- Relationship to study treatment or other causality
- Outcome

For SAEs, events occurring secondary to the primary event should be captured and reported via the established safety reporting mechanism.

The following should be considered when recording SAEs:

- Death is an outcome of an event. The event that resulted in the death should be recorded and reported on the eCRF.
- For hospitalizations, surgical, or diagnostic procedures, the illness leading to the surgical or diagnostic procedure should be recorded as the SAE, not the procedure

itself. The procedure should be captured in the narrative as part of the action taken in response to the illness.

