6.3.1. Adverse Events

6.3.1.1. All TEAEs

All TEAEs will be summarized by SOC and PT. This summary table and all other TEAE summaries by SOC and PT will be presented by descending frequency in the etrasimod group.

All AEs, regardless of treatment-emergent status, will be included in an AE listing. Additionally, a listing of other AE details as collected on the CRF will be presented. Exposure-adjusted incidence rate (EAIR) of TEAEs will be summarized by SOC and PT. Exposure is defined as the sum of either time (year) from first dose to the onset of first such event for those who experienced this AE, or time (year) from first dose to last participation for those who did not experience this AE. The EAIR is calculated as the number of participants with the AE divided by the total exposure in participant-years.

Severity

All TEAEs will be summarized by SOC, PT, and maximum severity, with SOC and PT presented by descending frequency. If a participant reports a TEAE more than once within a SOC/PT, the AE with the worst-case severity will be used in this summary.

Relationship to Study Treatment

All related TEAEs will be summarized by SOC, PT, and maximum severity, with SOC and PT presented by descending frequency. If a participant reports a TEAE more than once within a SOC/PT, the AE with the worst-case severity will be used in this summary. A "related TEAE" for the purpose of this summary is defined as a TEAE with relationship to study treatment of "probably related" or "related".

6.3.1.2. TEAEs Leading to Discontinuation of Study Treatment and TEAEs Leading to Interruption of Study Treatment

All TEAEs leading to discontinuation of study treatment will be summarized by SOC and PT. TEAEs leading to interruption of study treatment will be summarized by SOC and PT as well.

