6.3.1.4. TEAEs of Special Interest

TEAEs of special interest will be summarized by category, subcategory, and PT by descending frequency by treatment group.

For each category, subcategory, and PT, model-based analysis will be performed to compare treatment effect between etrasimod and placebo. An extended Cox regression model will be used to handle recurring AEs (Cao 2011, Section 8 References). The stratification variables, naïve to biologic or JAK inhibitor therapy status at study entry (Yes or No) and Baseline corticosteroid use (Yes or No), will be included in the model. A participant with K events contributes (K+1) observations to the input data set; here K might be 0. The k-th observation of the participant identifies the time interval from the start date of the (k-1)-th event, or time 0 (if k = 1), to the start date of the kth event, k = 1, ..., K. The (K+1)-th observation represents the time interval from the K-th event to the date of censorship, ie, the date of last dose or date of last study visit up to Week 52, whichever is later. Hazard ratios (Etrasimod group vs placebo group), 95% CIs, and 2-sided p-values for treatment effect comparison will be presented.

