9.1.5. Partial Date Convention

Imputed dates will NOT be presented in the listings.

Table 10. Algorithm for Treatment Emergence of Adverse Events

Start Date	Stop Date	Action
Known	Known, Partial, or Missing	 If AE start date < study treatment first dose date, then not TEAE If AE start date ≥ study treatment first dose date, then TEAE
Partial, but known components show that it cannot be on or after date of first dose of study treatment	Known, Partial, or Missing	Not TEAE
Partial, could be on or after date of first dose of study treatment	Known	If AE stop date < study treatment first dose date, then not TEAE

Table 10. Algorithm for Treatment Emergence of Adverse Events

Start Date	Stop Date	Action
		If AE stop date ≥ study treatment first dose date, then TEAE
	Partial	Impute AE stop date as latest possible date (ie, last day of month if day unknown or 31st December if day and month are unknown), then: • If AE stop date < study treatment first dose date, then not TEAE • If AE stop date ≥ study treatment first dose date, then TEAE
	Missing	Assumed TEAE

Table 11. Algorithm for Prior and Concomitant medications

Start Date	Stop Date	Action
Known	Known	If medication stop date < study treatment first dose date, assign as prior
		If medication stop date ≥ study treatment first dose date, assign as concomitant
	Partial	 Impute stop date as latest possible date (ie, last day of month if day unknown or 31st December if day and month are unknown), then: If medication stop date < study treatment first dose date, assign as prior If medication stop date ≥ study treatment first dose date, assign as concomitant
	Missing	If medication stop date is missing could never be assumed a prior medication, assign as concomitant
Partial	Known	 Impute start date as earliest possible date (ie, first day of month if day unknown or 1st January if day and month are unknown), then: If medication stop date < study treatment first dose date, assign as prior If medication stop date ≥ study treatment first dose date, assign as concomitant

Table 11. Algorithm for Prior and Concomitant medications

Start Date	Stop Date	Action

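### The TEAE rule has no end date: events starting on open-label etrasimod could be counted under placebo, and the special-interest Cox model can produce a negative interval

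*SAP*

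**What the plan says.** **The flag.** SAP 3.2.2.1 states: "Treatment-emergent adverse events (TEAEs) are defined as AEs that started or worsened in severity on or after the first dose of study treatment". The programming rule in SAP 9.1.5, Table 10, matches it: "If AE start date ≥ study treatment first dose date, then TEAE". Neither refers to the last dose or to entry into the open-label extension (OLE). Doubtful cases go one way: "In the case where it is not possible to define an AE as treatment-emergent or not, the AE will be classified as treatment-emergent".

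**The recording period.** Under Protocol 9.9.9.2.2, adverse event recording starts at consent and "continues up to 30 days after the last administration of study treatment". That section makes no exception for participants who roll over.

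**The rollover.** Protocol 5.1.1 says: "The Day 1 visit of the OLE study must occur within 14 days of the last on treatment visit of this study". Where there is a gap, "the subject should continue their double-blind study treatment from Study APD334-210 until the day before the W0/D1 visit". The footnotes to the protocol's Table 6 also allow for entry on the day of the Week 52 visit.

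**Exposure and censoring.** For the exposure-adjusted incidence rate (EAIR), SAP 6.3.1.1 counts time to the first event, "or time (year) from first dose to last participation for those who did not experience this AE". The end point of that second clock is not defined. For events of special interest, SAP 6.3.1.4 fits an extended Cox model in which the interval after a participant's last event ends at the censoring date, "ie, the date of last dose or date of last study visit up to Week 52, whichever is later".

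**Attribution.** The Safety Set analyses participants by treatment received, and the outputs for treated participants have two columns, Etrasimod and Placebo (SAP Section 4 and Table 13). No rule reassigns or drops an event that starts on open-label drug.

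**The concern.** Read together, these rules let an event that starts on open-label etrasimod be treatment-emergent in this study and be shown under placebo. The days concerned include a placebo participant's first exposure to etrasimod. Protocol 1.3 lists first-dose bradycardia and atrioventricular block among the events reported with this drug class, and SAP 3.2.2.1 makes bradycardia and conduction delay events of special interest. Charging such events to placebo would narrow the safety contrast for the events the plan watches most closely.

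The Cox model has a separate difficulty. Its censoring date can fall before events that the flag admits, so its input data can be impossible even if nobody rolls over.

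**Working it through.** The plan gives no figure to reproduce here. The check is date arithmetic, followed by an illustration.

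**1. Overlap with open-label treatment.** Let L be the day of the last blinded dose.
- In the gap case, OLE Day 1 = L + 1 (Protocol 5.1.1). That open-label dosing starts on Day 1 is inferred from the instruction to stop blinded drug the day before.
- Adverse event recording ends at L + 30 (Protocol 9.9.9.2.2).
- Overlap = L + 1 to L + 30 = 30 days, whether the visit-to-OLE gap is 1 day or 14, because blinded drug fills it. Same-day entry also leaves no drug-free interval.
- As a share of blinded treatment: 30/364 = 8.2% for a Week 52 completer, and 30/84 = 35.7% for someone who rolls over at Week 12.

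**2. Illustration of size.** Planned placebo number: 75 (SAP 2.3). Neither the rollover share r nor the 30-day probability q of a first event of a given type on open-label etrasimod is in the documents. Both are assumptions, and full recording in this study's case report form is a third.
- Open-label person-years inside the placebo recording window = 75 × r × 30/365.25. For r = 0.25 this is 1.5, and for r = 0.75 it is 4.6.
- Extra placebo participants with an event = 75 × r × q.
- Shift in the etrasimod-minus-placebo risk difference = −r × q, with the etrasimod arm held fixed.

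| r | q | Extra placebo participants | Shift (percentage points) |
|---|---|---|---|
| 0.25 | 0.02 | 0.4 | −0.5 |
| 0.50 | 0.05 | 1.9 | −2.5 |
| 0.75 | 0.10 | 5.6 | −7.5 |

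Etrasimod-arm rollovers would bring their own 30 days, which would offset part of the shift for ordinary events. The offset should be smaller for first-dose effects, since those participants are already on drug. If post-rollover events are not recorded in this study, every entry is zero.

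**3. Cox model, no rollover involved.** Take a completer with last dose and Week 52 visit both on Day 365 who does not enter the OLE and has an event of special interest on Day 380 (an invented example).
- Recorded: 380 − 365 = 15 days, within 30.
- Treatment-emergent: 380 is after first dose.
- Censoring date: the later of Day 365 and Day 365, so Day 365.
- With K = 1, the final interval runs from Day 380 to Day 365, which is −15 days.

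The first interval, ending in the event on Day 380, would also stay in the data, although participants without an event leave the risk set by Day 365. Time after Week 52 would then be contributed only by participants who have events. For early stoppers the conflict depends on whether a follow-up visit before Week 52 counts as a study visit, which the SAP does not say.

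**4. EAIR.** A follow-up event counts in the numerator. For participants without the event, exposure could end at last dose, at last visit, or at the end of adverse event recording, because *last participation* is undefined. The rate depends on which is programmed.

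**The case against.** The strongest objection is that the misattribution needs a data flow nobody has shown. The OLE is a separate study with its own Day 1, and its protocol is not among these documents. The SAP identifies serious, fatal and withdrawal events from the Adverse Events case report form. Rollovers have no 2- or 4-week follow-up visit here (Protocol 9.5), events are elicited at visits, and Protocol 9.9.9.2.2 lifts the duty to seek events actively once participation has ended. Protocol 9.5 repeats the 30-day instruction in a section that opens with participants not entering the OLE. The SAP's output periods include no open-label period.

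Much of this stands, and it is why the size may be nil. None of it is an exclusion rule, though. Section 9.9.9.2.2 is general, and it also requires serious events suspected to be related to treatment to be reported whenever they occur. Elsewhere the SAP does draw the line: follow-up pharmacokinetic samples are limited to participants not in an extension study (3.2.3, 6.2), and exposure beginning on or after the last study treatment is not rescue therapy (9.3). The adverse event flag has no counterpart.

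It can also be said that a Week 52 Cox window beside a longer incidence table is a legitimate choice. It is, provided later events are excluded from the model, and the SAP does not say they are.

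A reader might infer three competing end dates. That goes too far: a risk difference has no exposure denominator, so it supplies no rival end date. Nor are events admitted without limit. The recording period bounds the flag in practice, apart from suspected-related serious events reported later.

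**Conclusion.** The point holds as a defect in the written rules. Followed literally, they allow up to 30 days of open-label etrasimod per rollover participant to be reported under the blinded arm, and they can generate a negative Cox interval for an ordinary follow-up event. The second finding rests on the text alone. The first has an effect only if post-rollover events reach this study's database, which the documents leave open.

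A reader might conclude that the safety comparison is biased toward no difference. The documents do not support that. They show that it could be, by an unknown amount that includes zero; the range of 0.4 to 5.6 placebo participants rests wholly on assumed rates and full recording. A reader might also conclude that the first-dose cardiac analyses are contaminated. They are not: the Holter endpoints use Day 1 recordings, and the minimum heart rate summaries are tied to Day 1 of this study (SAP Section 4, 6.3.2.3 and 6.3.2.4). The exposed outputs are the adverse event incidence tables, risk differences and EAIRs.

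The correction should be made, because the rules can misattribute events and the remedy is small.

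**What to change.** - In SAP 3.2.2.1, define a treatment-emergent event as onset or worsening from first dose to the earlier of (a) last double-blind dose plus 30 days and (b) the day before the first OLE dose. Participants who do not roll over keep the full 30 days; for rollovers the overlap falls from 30 days to 0.
- Put the same end date in Table 10.
- Replace *last participation* in the EAIR definition with that date, capped at the end of study participation.
- Use that date as the Cox censoring date in SAP 6.3.1.4. Alternatively, keep the Week 52 rule and state that events after it are excluded from that model.
- State that events starting on open-label drug are reported in the OLE study.

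The cost is SAP wording and one date derivation. The last-dose date already comes from the End of Study form (SAP 6.5.3.1). The first OLE dose date may have to be brought in from APD334-303. Rollovers will have shorter post-treatment observation than other participants, which is why the EAIR must use the same end date.
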